8.3. Clinical Laboratory Tests

8.3.1. Laboratory Value Definitions

Laboratory values, change from baseline values, and percent change from baseline values will be summarized descriptively by visit. Change from baseline will be defined as:

Change from baseline = observed value at timepoint – baseline value

Percent change from baseline will be defined as:

Percent change from baseline = $100 \times (\text{observed value at timepoint} - \text{baseline value}) / \text{baseline value}$

Baseline will be determined according to Section 4.1.3.

The baseline value will be determined using the nonmissing values collected before the first dose, prioritizing scheduled assessments for baseline identification over unscheduled visits. The last record before administration in the highest priority will be considered the baseline record.

Laboratory test values will be assessed for severity based on the numerical component of CTCAE v5.

8.3.2. Laboratory Value Summaries

Any laboratory test results and associated normal ranges from local laboratories will be converted to SI units, if needed.

When there are multiple nonmissing laboratory values for a participant's particular test within a visit window, the convention described in Table 3 will be used to determine the record used for by-visit tabulations and summaries.

Table 3: Identification of Records for Postbaseline By-Visit Summaries

Priority	Laboratory Visit	Proximity to Visit Window	Tiebreaker
1	Scheduled	In-window	Use smallest laboratory sequence number
2	Unscheduled	In-window	
3	Scheduled	Out-of-window	

Shift tables based on the worst postbaseline value recorded will use all postbaseline values. The denominator for the percentage calculation will use the number of participants in the baseline category as the denominator for the percentage in each of the categories during the study.

Numeric laboratory values will be summarized descriptively in SI units, and non-numeric test values will be tabulated when necessary.

Severity grades will be assigned to laboratory test values based on the numerical component of CTCAE v5. Shift tables will be presented showing change in CTCAE grade from baseline to worst grade postbaseline. Separate summaries for abnormally high and abnormally low laboratory values will be provided when the laboratory parameter has both high and low grading criteria. The denominator for the percentage calculation will be the number of participants in the baseline category. The number of participants who had worsening of laboratory abnormalities will be summarized by maximum severity.

All clinical laboratory data will be listed.

8.3.3. Potential Hy's Law Events

Participants with elevated ALT or AST $> 3 \times$ ULN range and alkaline phosphatase $< 2 \times$ ULN range accompanied by total bilirubin $> 2 \times$ ULN range will be listed by treatment group.

8.4. Vital Signs

Values at each scheduled visit, change, and percentage change from baseline for vital signs, including pulse, respiratory rate, and temperature, will be summarized descriptively. Change from baseline will be defined as:

Change from baseline = observed value at timepoint – baseline value

Percent change from baseline will be defined as:

Percent change from baseline = $100 \times (\text{observed value at timepoint} - \text{baseline value}) / \text{baseline value}$

For vital signs including systolic blood pressure, diastolic blood pressure, and body weight, shift tables will be presented showing change in CTCAE grade from baseline to worst grade postbaseline. Severity grades will be assigned to these values based on the numerical component of CTCAE v5.

For participants exhibiting vital sign abnormalities, the abnormal values will be listed along with their assigned treatment group.

8.5. Electrocardiograms

Twelve-lead ECGs including heart rate and PR, RR, QT, QRS, QT, QTcB, and QTcF intervals will be obtained for each participant during the study. Values at each scheduled visit, change, and percentage change from baseline will be summarized for each ECG parameter. Baseline will be the last value collected before the first dose of study treatment. Change from baseline will be defined as:

Change from baseline = observed value at timepoint – baseline value

Percent change from baseline will be defined as:

$$\text{Percent change from baseline} = 100 \times (\text{observed value at timepoint} - \text{baseline value}) / \text{baseline value}$$

Normal ranges for ECG values are defined in [Table 4](#). ECG values will also be considered abnormal if the absolute percentage change from baseline is more than 25% (30% for QRS interval). Participants exhibiting ECG abnormalities will be listed with study visit and assigned treatment group. Abnormal values for participants with alert ECG values, defined as both the absolute value and the percentage change from baseline being outside normal ranges, will be identified and listed. Outliers of QT, QTcB, and QTcF values, defined as absolute values > 450 milliseconds, > 470 milliseconds, > 500 milliseconds, respectively, or change from baseline > 30 milliseconds, will be summarized.

Table 4: Normal Ranges for Electrocardiogram Intervals

Parameter	High Threshold	Low Threshold
PR	≤ 200 ms	≥ 120 ms
RR	≤ 1200 ms	≥ 600 ms
QT (male)	≤ 450 ms	≥ 350 ms
QT (female)	≤ 460 ms	≥ 360 ms
QRS	≤ 100 ms	≥ 60 ms
QTcB, QTcF	≤ 450 ms	≥ 295 ms

Interpretation of ECGs will be summarized by number and percentage. Clinically significant abnormalities will be summarized by count and percentage by visit. Specific abnormalities will be listed.

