3.4.2	Shift Summary of Diastolic Blood Pressure in CTCAE Grade - To the Worst Abnormal Value	Safety
3.4.3	Summary of Pulse	Safety
3.4.4	Summary of Respiratory Rate	Safety
3.4.5	Summary of Body Temperature	Safety
3.4.6	Shift Summary of Body Weight in CTCAE Grade - To the Worst Abnormal Value	Safety
3.5.1	Summary of PR Interval (ms) From 12-Lead ECG	Safety
3.5.2	Summary of RR Interval (ms) From 12-Lead ECG	Safety
3.5.3	Summary of QRS Interval (ms) From 12-Lead ECG	Safety
3.5.4	Summary of QT Interval (ms) From 12-Lead ECG	Safety
3.5.5	Summary of QTcB Interval (ms) From 12-Lead ECG	Safety

Table No.	Title	Population
3.5.6	Summary of QTcF Interval (ms) From 12-Lead ECG	Safety
3.5.7	Summary of Heart Rate (bpm) From 12-Lead ECG	Safety
3.5.8	Summary of Outliers of QT, QTcB, and QTcF Interval Values (ms) From 12-Lead ECG	Safety
3.5.8	Summary of Clinically Significant ECG Abnormality	Safety
3.5.9	Summary of ECG Interpretation	Safety
3.6.1	Summary of Delay Time in Planned Radical Cystectomy	Safety
3.6.2	Summary of Reasons for Delay in Planned Radical Cystectomy	Safety

Listings

Listing No.	Title
2.1.1	Informed Consent
2.1.2	Disposition
2.1.3	Radical Cystectomy
2.1.4	Delay in Cystectomy
2.1.5	Last Dose Administration and Radical Cystectomy Delay
2.1.6	Staging of Bladder Cancer Pre- and Post-Radical Cystectomy
2.1.7	End of Study Details
2.1.8	Post-Therapy
2.2.1	Inclusion/Exclusion Criteria
2.2.2	Protocol Deviations
2.3.1	Analysis Populations
2.4.1	Demographics and Baseline Characteristics
2.4.2.1	Urothelial Cancer History: Previous Urothelial Cancer History
2.4.2.2	Urothelial Cancer History: MIBC Current Diagnosis
2.4.2.3	Urothelial Cancer History: TURBT Diagnosis Method
2.4.3	Prior Radiation Treatment
2.4.4	Prior Systemic Therapy
2.4.5	Prior Surgery or Surgical Procedure for Disease Under Study
2.4.6	Procedures and Nondrug Therapy
2.4.7	Medical History
2.4.8	Prior and Concomitant Medications
2.5.1	Study Drug Compliance
2.5.2	Study Drug Administration - Epacadostat
2.5.3	Study Drug Administration - Retifanlimab
2.5.4	Study Drug Administration - INCAGN02385
2.5.5	Study Drug Administration - INCAGN02390
2.6.1	Deaths
2.6.2	Overall Response Assessment by Visit
2.6.3	Response Assessment
2.6.4	Pathological Complete Response
2.6.5	Major Pathological Response
2.6.6	ECOG Status
2.7.1	Adverse Events
2.7.2	Serious Adverse Events

Listing No.	Title
2.7.3	Grade 3 and Higher Adverse Events
2.7.4	Fatal Adverse Events
2.7.5.1	Adverse Events Leading to Study Treatment Discontinuation

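### The ECG outlier count takes no account of baseline, so Table 3.5.8 mixes prolongation present before the first dose with prolongation that appears on treatment

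*SAP*

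**What the plan says.** Section 8.5 of the SAP gives the rule for QT, QTcB and QTcF outliers, an absolute criterion followed by an alternative, as "defined as absolute values > 450 milliseconds, > 470 milliseconds, > 500 milliseconds, respectively, or change from baseline > 30 milliseconds, will be summarized". Either is enough. Taken in the order given, the cut-offs are QT > 450 ms, QTcB > 470 ms and QTcF > 500 ms.

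The same section fixes the ECG baseline: "Baseline will be the last value collected before the first dose of study treatment". The value needed to condition on is therefore already defined for each participant.

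Appendix A plans one display for this rule, on the Safety Population: "Summary of Outliers of QT, QTcB, and QTcF Interval Values (ms) From 12-Lead ECG". It is the first of two tables numbered 3.5.8; the second covers clinically significant ECG abnormalities. No shift table is listed for QT, QTcB or QTcF.

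Elsewhere the SAP does bring baseline in:

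- Section 8.3.2, laboratory values: "Shift tables will be presented showing change in CTCAE grade from baseline to worst grade postbaseline". Appendix A lists these tables for hematology and chemistry.
- Section 8.4, blood pressure and body weight: "shift tables will be presented showing change in CTCAE grade from baseline to worst grade postbaseline".
- Section 8.5 itself, alert ECG values, which go to a listing: "defined as both the absolute value and the percentage change from baseline being outside normal ranges".

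**The concern.** A table of outliers by treatment group is normally read as showing what happened on each regimen. Under this rule it also shows who entered each group with a long interval. Someone above the cut-off before dosing needs no change at all to be counted, and can be counted while improving. Once the two criteria are combined in one count, the reader cannot tell a stable high baseline from a rise on treatment.

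What is at stake is how Table 3.5.8 is read. The groups are small, so one or two pre-existing cases can make regimens look different. No hypothesis test or decision rule in the SAP uses this table.

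**Working it through.** The SAP gives no figure that depends on this rule, so there is none to reproduce. The check applies the rule to example values and then sizes one case.

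**Inputs.** Cut-offs, the or, and the baseline definition come from section 8.5. Planned group sizes come from section 3.3, Table 2: 18 in each of A, B, D and E, and 9 in C. The share of participants above a cut-off at baseline is not in the SAP.

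**Rule as written:** outlier if value > cut-off, or value − baseline > 30 ms.

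**Comparison rule, new exceedances only:** outlier if (value > cut-off and baseline ≤ cut-off), or value − baseline > 30 ms.

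| Interval | Baseline (ms) | On treatment (ms) | Change (ms) | As written | New exceedances only |
|---|---|---|---|---|---|
| QT | 460 | 460 | 0 | outlier | no |
| QT | 460 | 452 | −8 | outlier | no |
| QTcB | 475 | 475 | 0 | outlier | no |
| QTcF | 505 | 505 | 0 | outlier | no |
| QT | 445 | 455 | +10 | outlier | outlier |
| QT | 400 | 431 | +31 | outlier | outlier |
| QT | 460 | 491 | +31 | outlier | outlier |
| QTcB | 475 | 500 | +25 | outlier | no |

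The first four rows are counted on the absolute criterion alone. Their changes are 0% to 2% in size (8/460 = 1.7%), below the 25% limit in section 8.5, so none would be an alert value. The last row shows the weakness of the comparison rule: a participant who starts above the cut-off and rises by 25 ms leaves the count.

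**Size of one case.** 1/18 = 5.6 percentage points in A, B, D or E; 1/9 = 11.1 points in C. The actual Safety Population denominators may differ from the planned sizes.

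**Illustration of frequency, on assumptions only.** If a proportion p of participants sits above a cut-off both at baseline and after dosing, with no drug effect, a group of n expects n × p baseline-only outliers, and the chance of at least one is 1 − (1 − p)^n.

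| p (assumed) | n = 18: expected | n = 18: at least one | n = 9: expected | n = 9: at least one |
|---|---|---|---|---|
| 2% | 0.36 | 31% | 0.18 | 17% |
| 5% | 0.9 | 60% | 0.45 | 37% |
| 10% | 1.8 | 85% | 0.9 | 61% |
| 20% | 3.6 | 98% | 1.8 | 87% |

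A second route assumes a normal baseline QTcB. With mean/SD of 415/20, 425/25 and 435/30 ms, the share above 470 ms is 0.3%, 3.6% and 12.2%, and the chance of at least one in 18 is 5%, 48% and 90%. For the harm described these are upper bounds, because the value must also stay above 470 ms after dosing. The higher cut-off gives much less: at mean 425 and SD 25, the share above 500 ms is 0.13%, or about 2% for at least one in 18.

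**The case against.** The case for leaving the rule alone is reasonable. An absolute criterion plus a change criterion is coherent and can be programmed, and over-inclusion is defensible in a safety screen. The SAP nowhere promises a treatment-emergent ECG count, so nothing is contradicted. It also uses absolute limits without baseline elsewhere: the potential Hy's Law listing in section 8.3.3 has no baseline condition, and coagulation, thyroid and lipid values get no shift table. Section 8.5 already summarizes change and percentage change by visit for each ECG parameter, and Listings 2.10.1 and 2.10.2 cover the individual ECG values and the abnormal ones. The table shells are in a separate document and may already split the rows.

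Most of this stands, and it limits the point to a minor one. It does not remove it. The value summaries and listings let a reader trace a case, but they leave the count in Table 3.5.8 as it is, and the SAP text does not ask the shells for a baseline split.

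Four stronger readings are tempting, and the SAP does not support them:

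- **That the count will be materially inflated.** The ranges above rest wholly on assumed values. Unseen eligibility limits could make high baselines rare, particularly QTcF above 500 ms.
- **That the groups will be biased.** Assignment is randomized within PD-L1 strata, so pre-existing prolongation produces chance imbalance, which matters only because the groups are small.
- **That the SAP uses baseline for all other safety data and overlooks it for ECG.** It uses both styles, as noted above.
- **That predose values themselves are meant to be counted.** The sentence does not say postbaseline, but silence is not evidence of that intention.

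**Conclusion.** The point holds as a minor improvement to a descriptive safety table. As written, the absolute criterion alone makes an outlier, without reference to baseline, so Table 3.5.8 combines two different things: prolongation carried into the trial and prolongation that appears on treatment. That conclusion follows from the wording of section 8.5 and the absence of an ECG shift table in Appendix A, and needs no assumption beyond taking the cut-offs in the order stated.

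Each such participant moves the group percentage by 5.6 points (18) or 11.1 points (9) at the planned sizes. How many there will be is unknown from the SAP. No primary or secondary efficacy conclusion is affected.

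**What to change.** In section 8.5 and the outlier Table 3.5.8, for each of QT, QTcB and QTcF:

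1. Cross-tabulate baseline category (above / not above the cut-off) by worst postbaseline category. This is the approach of sections 8.3.2 and 8.4 for hematology, chemistry, blood pressure and weight, and section 8.3.2 already supplies a denominator rule (the number in the baseline category).
2. Report the number with a change above 30 ms on a separate line.

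Do not substitute a count of new exceedances only, since participants who start above the cut-off and rise by 30 ms or less would disappear from it. The cross-tabulation keeps everyone with a baseline and a postbaseline value.

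The cost is a change to the outlier sentence in 8.5 and one table shell; the baseline ECG is already defined in the plan. One limit remains: a participant going from 475 to 500 ms and one staying at 475 ms fall in the same above/above cell, so smaller rises from a high baseline must still be read from the change summaries and listings.

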9. INTERIM ANALYSES

There are no planned, formal interim analyses for this study. Periodic review of accrued clinical data will be conducted in accordance with the DSMB charter.

10. CHANGES AND MODIFICATIONS TO THE ANALYSIS PLAN

All versions of the SAP are listed in [Table 5](#).

Table 5: Statistical Analysis Plan Versions

SAP Version	Date
Original	27 MAR 2024

10.1. Changes to Protocol-Defined Analyses

The following differ from those described in the Protocol:

- The primary efficacy endpoint will be fold change from baseline instead of change from baseline in the number of CD8+ lymphocytes.
- The SAP changed CD8+ T effector cells to CD8+ lymphocytes for consistency.
- [REDACTED]
- The definitions of the Translational-Evaluable and Efficacy Populations were updated.

10.2. Changes to the Statistical Analysis Plan

Not applicable.

APPENDIX A. PLANNED TABLES AND LISTINGS

This appendix provides a list of the planned tables and listings for the Clinical Study Report. Shells are provided in a separate document.

The lists of tables and listings are to be used as guidelines. Modifications of the lists that do not otherwise affect the nature of the analysis will not warrant an amendment to the SAP.

Tables

Table No.	Title	Population
Baseline and Demographic Characteristics		
1.1.1	Analysis Populations	All-Screened
1.1.2	Summary of Participant Disposition	FAS
1.1.3	Summary of Number of Participants Enrolled by Country and Site	FAS
1.1.4	Summary of Protocol Deviations	FAS
1.2.1	Summary of Demographics and Baseline Characteristics	FAS
1.3.1	Summary of Cancer History and Baseline Disease Characteristics	FAS
1.4.1	Summary of Prior Medications	FAS
1.4.2	Summary of Concomitant Medications	FAS
1.5.1	Summary of General Medical History	FAS
1.5.2	Summary of Prior Systemic Cancer Therapy	FAS
1.5.3	Summary of Prior Radiotherapy and Procedures	FAS
Efficacy		
2.1	Summary of Fold Change From Baseline in the Number of CD8+ Lymphocytes	Translational-Evaluable
2.2	Summary of Pathological Complete Response Rate	Efficacy
2.3	Summary of Major Pathological Response	Efficacy
Safety		
3.1.1.1	Summary of Exposure and Duration of Exposure to Epacadostat	Safety
3.1.1.2	Summary of Exposure and Duration of Exposure to Retifanlimab	Safety
3.1.1.3	Summary of Exposure and Duration of Exposure to INCAGN02385	Safety
3.1.1.4	Summary of Exposure and Duration of Exposure to INCAGN02390	Safety
3.1.2	Summary of Epacadostat Compliance	Safety
3.2.1	Overall Summary of Treatment-Emergent Adverse Events	Safety
3.2.2	Summary of Treatment-Emergent Adverse Events by MedDRA System Organ Class and Preferred Term	Safety
3.2.3	Summary of Treatment-Emergent Adverse Events by MedDRA Preferred Term in Decreasing Order of Frequency	Safety
3.2.4	Summary of Treatment-Emergent Adverse Events by MedDRA System Organ Class, Preferred Term, and Maximum Severity	Safety
3.2.5	Summary of Grade 3 or Higher Treatment-Emergent Adverse Events by MedDRA System Organ Class and Preferred Term	Safety
3.2.6	Summary of Grade 3 or Higher Treatment-Emergent Adverse Events by MedDRA Preferred Term in Decreasing Order of Frequency	Safety
3.2.7	Summary of Serious Treatment-Emergent Adverse Events by MedDRA System Organ Class and Preferred Term	Safety
3.2.8	Summary of Treatment-Emergent Serious Adverse Events by MedDRA Preferred Term in Decreasing Order of Frequency	Safety

Table No.	Title	Population
3.2.9	Summary of Treatment-Related Treatment-Emergent Adverse Events by MedDRA System Organ Class and Preferred Term	Safety
3.2.10	Summary of Treatment-Related Treatment-Emergent Adverse Events by MedDRA Preferred Term in Decreasing Order of Frequency	Safety
3.2.11	Summary of Investigator Assessed Immune-Related Treatment-Emergent Adverse Events by MedDRA System Organ Class and Preferred Term	Safety
3.2.12	Summary of Investigator Assessed Immune-Related Treatment-Emergent Adverse Events of Grade 3 or Higher by MedDRA System Organ Class and Preferred Term	Safety
3.2.13	Summary of Treatment-Related Serious Treatment-Emergent Adverse Events by MedDRA System Organ Class and Preferred Term	Safety
3.2.14	Summary of Treatment-Related Serious Treatment-Emergent Adverse Events by MedDRA Preferred Term in Decreasing Order of Frequency	Safety
3.2.15	Summary of Treatment-Emergent Adverse Events With a Fatal Outcome by MedDRA System Organ Class and Preferred Term	Safety
3.2.16	Summary of Nonserious Treatment-Emergent Adverse Events by MedDRA System Organ Class and Preferred Term	Safety
3.2.17	Summary of Treatment-Emergent Adverse Events Leading to Dose Interruption by MedDRA System Organ Class and Preferred Term	Safety
3.2.18	Summary of Treatment-Emergent Adverse Events Leading to Discontinuation of Study Treatment by MedDRA System Organ Class and Preferred Term	Safety
3.2.19	Summary of Treatment-Emergent Adverse Events That Caused Delay in Radical Cystectomy by MedDRA System Organ Class and Preferred Term	Safety
3.2.20	Summary of Treatment-Emergent Adverse Events Considered as Post-Radical Cystectomy Complications by MedDRA System Organ Class and Preferred Term	Safety
3.3.1.1	Summary of Laboratory Values - Hematology	Safety
3.3.1.2	Summary of Laboratory Values - Chemistry	Safety
3.3.1.3	Summary of Laboratory Values - Coagulation	Safety
3.3.1.4	Summary of Laboratory Values - Thyroid Panel	Safety
3.3.1.5	Summary of Laboratory Values - Lipids	Safety
3.3.2.1	Shift Summary of Hematology Laboratory Values in CTCAE Grade - To the Worst Abnormal Value	Safety
3.3.2.2	Shift Summary of Chemistry Laboratory Values in CTCAE Grade - To the Worst Abnormal Value	Safety
3.4.1	Shift Summary of Systolic Blood Pressure in CTCAE Grade - To the Worst Abnormal Value	Safety
3.4.2	Shift Summary of Diastolic Blood Pressure in CTCAE Grade - To the Worst Abnormal Value	Safety
3.4.3	Summary of Pulse	Safety
3.4.4	Summary of Respiratory Rate	Safety
3.4.5	Summary of Body Temperature	Safety
3.4.6	Shift Summary of Body Weight in CTCAE Grade - To the Worst Abnormal Value	Safety
3.5.1	Summary of PR Interval (ms) From 12-Lead ECG	Safety
3.5.2	Summary of RR Interval (ms) From 12-Lead ECG	Safety
3.5.3	Summary of QRS Interval (ms) From 12-Lead ECG	Safety
3.5.4	Summary of QT Interval (ms) From 12-Lead ECG	Safety
3.5.5	Summary of QTcB Interval (ms) From 12-Lead ECG	Safety

Table No.	Title	Population
3.5.6	Summary of QTcF Interval (ms) From 12-Lead ECG	Safety
3.5.7	Summary of Heart Rate (bpm) From 12-Lead ECG	Safety
3.5.8	Summary of Outliers of QT, QTcB, and QTcF Interval Values (ms) From 12-Lead ECG	Safety
3.5.8	Summary of Clinically Significant ECG Abnormality	Safety
3.5.9	Summary of ECG Interpretation	Safety
3.6.1	Summary of Delay Time in Planned Radical Cystectomy	Safety
3.6.2	Summary of Reasons for Delay in Planned Radical Cystectomy	Safety

Listings

Listing No.	Title
2.1.1	Informed Consent
2.1.2	Disposition
2.1.3	Radical Cystectomy
2.1.4	Delay in Cystectomy
2.1.5	Last Dose Administration and Radical Cystectomy Delay
2.1.6	Staging of Bladder Cancer Pre- and Post-Radical Cystectomy
2.1.7	End of Study Details
2.1.8	Post-Therapy
2.2.1	Inclusion/Exclusion Criteria
2.2.2	Protocol Deviations
2.3.1	Analysis Populations
2.4.1	Demographics and Baseline Characteristics
2.4.2.1	Urothelial Cancer History: Previous Urothelial Cancer History
2.4.2.2	Urothelial Cancer History: MIBC Current Diagnosis
2.4.2.3	Urothelial Cancer History: TURBT Diagnosis Method
2.4.3	Prior Radiation Treatment
2.4.4	Prior Systemic Therapy
2.4.5	Prior Surgery or Surgical Procedure for Disease Under Study
2.4.6	Procedures and Nondrug Therapy
2.4.7	Medical History
2.4.8	Prior and Concomitant Medications
2.5.1	Study Drug Compliance
2.5.2	Study Drug Administration - Epacadostat
2.5.3	Study Drug Administration - Retifanlimab
2.5.4	Study Drug Administration - INCAGN02385
2.5.5	Study Drug Administration - INCAGN02390
2.6.1	Deaths
2.6.2	Overall Response Assessment by Visit
2.6.3	Response Assessment
2.6.4	Pathological Complete Response
2.6.5	Major Pathological Response
2.6.6	ECOG Status
2.7.1	Adverse Events
2.7.2	Serious Adverse Events

Listing No.	Title
2.7.3	Grade 3 and Higher Adverse Events
2.7.4	Fatal Adverse Events
2.7.5.1	Adverse Events Leading to Study Treatment Discontinuation
2.7.5.2	Adverse Events Leading to Delay of Radical Cystectomy
2.7.5.3	Adverse Events Leading to Hospitalization
2.7.6	Adverse Events Related to Post-Radical Cystectomy
2.7.7.1	Epacadostat-Related Adverse Events
2.7.7.2	Retifanlimab-Related Adverse Events
2.7.7.3	INCAGN02385-Related Adverse Events
2.7.7.4	INCAGN02390-Related Adverse Events
2.7.8	Infusion-Related Reactions
2.7.9	Postsurgical Complications Associated With Bladder Surgery
2.8.1	Clinical Laboratory Values - Hematology
2.8.2	Clinical Laboratory Values - Chemistry
2.8.3	Clinical Laboratory Values - Urinalysis
2.8.4	Clinical Laboratory Values - Coagulation
2.8.5	Clinical Laboratory Values - Thyroid Panel
2.8.6	Clinical Laboratory Values - Lipids
2.8.7	Clinical Laboratory Values - Serology
2.8.8	Abnormal Clinical Laboratory Values
2.8.9	Potential Hy's Law Events
2.8.10	Pregnancy Test
2.9.1	Vital Signs
2.9.2	Abnormal Vital Signs Values
2.10.1	12-Lead ECG Values
2.10.2	Abnormal 12-Lead ECG Values
2.11	Physical Examinations
2.12.1	Translational Assessments
2.12.2	RBC/Platelet Transfusions
2.12.3	Tissue Biopsies
2.12.4	HIV Management
2.12.5	COVID-19 Comments
2.12.6	Imaging

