Screening assessments may be completed over a period of up to 28 days. Treatment cycles are 28 days unless otherwise noted. Each participant enrolled in the study will receive a minimum of 1 treatment cycle if, in the judgment of the investigator, the participant has not met any criteria for study withdrawal. The treatment duration will be approximately 4 to 10 weeks. Radical cystectomy is typically scheduled for approximately 8 to 10 weeks with an average of 8 weeks from the TURBT (ie, approximately Day 56; [Poletajew et al 2014](#)).

Precystectomy assessments will be performed within 2 weeks before surgery. Participants will be followed for safety as well as radiographic imaging for 90 days after cystectomy or the last dose of study treatment in the event cystectomy is not performed.

Figure 1: Study Design Schema

¹ Treatment duration is based on date of radical cystectomy. Participants should receive a minimum of 4 weeks and maximum of 10 weeks of treatment.

The current sample size represents an estimated number of participants per treatment group in order to attain the necessary evaluable paired biopsies. Additional participants will be enrolled in treatment groups to ensure the number of evaluable paired biopsies are obtained. This is a platform design, and additional treatment arms may be added or prematurely stopped for enrollment.

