5. STATISTICAL METHODOLOGY

5.1. General Methodology

Unless otherwise noted, SAS software (SAS Institute Inc, Cary, NC; v9.4 or later) will be used for the generation of all tables, graphs, and statistical analyses. Descriptive summaries for continuous variables will include but not be limited to the number of observations, mean, standard deviation, median, minimum, and maximum. Descriptive summaries for categorical variables will include the number and percentage of participants in each category.

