5.3.6. Safety Population

The Safety Population will include all participants who received at least 1 dose of study treatment. Treatment groups for this population will be determined according to the actual treatment the participant received regardless of assigned study treatment.

All safety analyses will be conducted using the Safety Population.

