8.2.2. Adverse Events of Special Interest

Adverse events reported as post-radical cystectomy complications as well as those assessed as immune-related will be coded according to the MedDRA 26.0. Postsurgery complications will be further classified according to the Clavien-Dindo Grading System ([Dindo et al 2004](#)).

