8.2.3. Adverse Event Summaries

An overall summary of AEs by treatment group will include the following:

- Number (%) of participants who had any TEAEs
- Number (%) of participants who had any serious TEAEs
- Number (%) of participants who had any Grade 3 or higher TEAEs
- Number (%) of participants who had any TEAEs related to study treatment
- Number (%) of participants who had any immune-related TEAEs
- Number (%) of participants who had any immune-related TEAEs of Grade 3 or higher
- Number (%) of participants who permanently discontinued study treatment because of a TEAE
- Number (%) of participants who temporarily interrupted study treatment because of a TEAE
- Number (%) of participants who had any fatal TEAEs
- Number (%) of participants who had a delay in radical cystectomy due to a TEAE
- Number (%) of participants who had a TEAE leading to hospitalization

The following summaries will be produced by MedDRA term:

- Summary of TEAEs by MedDRA SOC and PT
- Summary of TEAEs by MedDRA PT in decreasing order of frequency
- Summary of TEAEs by MedDRA SOC, PT, and maximum severity
- Summary of Grade 3 or higher TEAEs by MedDRA SOC and PT
- Summary of Grade 3 or higher TEAEs by MedDRA PT in decreasing order of frequency
- Summary of serious TEAEs by MedDRA SOC and PT
- Summary of serious TEAEs by MedDRA PT in decreasing order of frequency
- Summary of treatment-related TEAEs by MedDRA SOC and PT
- Summary of treatment-related TEAEs by MedDRA PT in decreasing order of frequency
- Summary of immune-related TEAEs by MedDRA SOC and PT
- Summary of immune-related TEAEs of Grade 3 or higher by MedDRA SOC and PT
- Summary of treatment-related serious TEAEs by MedDRA SOC and PT
- Summary of treatment-related serious TEAEs by MedDRA PT in decreasing order of frequency

- Summary of nonserious TEAEs by MedDRA SOC and PT
- Summary of TEAEs leading to dose interruption by MedDRA SOC and PT
- Summary of TEAEs leading to discontinuation of study treatment by MedDRA SOC and PT
- Summary of TEAEs with a fatal outcome by MedDRA SOC and PT
- Summary of TEAEs by MedDRA SOC and PT leading to delay in radical cystectomy
- Summary of TEAEs considered as post-radical cystectomy complications by MedDRA SOC and PT

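### Table 3.2.20 reports post-cystectomy complications over all treated participants, so the percentage is diluted most in the group with the lowest proportion operated on

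*SAP*

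**What the plan says.** Section 8.2.3 of the SAP plans a "Summary of TEAEs considered as post-radical cystectomy complications by MedDRA SOC and PT". Appendix A lists it as Table 3.2.20, "Summary of Treatment-Emergent Adverse Events Considered as Post-Radical Cystectomy Complications by MedDRA System Organ Class and Preferred Term", and enters Safety in the population column.

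Section 5.3.6 defines that set without any surgical condition: "The Safety Population will include all participants who received at least 1 dose of study treatment". It then applies the set without exception: "All safety analyses will be conducted using the Safety Population". Participants are grouped there by the treatment they actually received.

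Section 5.1 sets the default form of such summaries: "Descriptive summaries for categorical variables will include the number and percentage of participants in each category". No analysis set in Section 5.3 is limited to participants who were operated on, and Section 8.2.3 gives no other base for this summary.

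The plan allows for treated participants without surgery. Section 3 sets follow-up at "90 days after cystectomy or the last dose of study treatment in the event cystectomy is not performed". Section 6.2 counts those who had a radical cystectomy, but in the disposition summary, which uses the FAS and the assigned group.

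Section 8.2.2 places these events under adverse events of special interest and adds: "Postsurgery complications will be further classified according to the Clavien-Dindo Grading System".

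**The concern.** Most safety tables rightly use all treated participants, because every treated participant can have the event. A post-cystectomy complication is different, since only someone who has had the operation can have one. With the Safety Population as the base, the percentage mixes two quantities: how often participants reach surgery, and how often surgery is followed by a complication.

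Two groups with the same surgical risk could then show different percentages only because different proportions were operated on. If toxicity kept participants from surgery in one group, that group's complication percentage would fall. What is at stake is how a descriptive safety table is read. No hypothesis test depends on it.

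**Working it through.** The SAP states no complication rate and no cystectomy rate, so there is no planned figure to reproduce. The check is an identity evaluated over assumed values.

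**Inputs**
- Planned group sizes (Section 3.3, Table 2): 18 participants in Groups A, B, D and E, and 9 in Group C.
- Planned paired biopsies (same table): 16 and 8. Section 5.3.5 counts a pair only if there is a surgical resection sample. The planned share of pairs, 16/18 = 8/9 = 88.9%, is therefore a document-based illustration of the operated share. It is not a stated cystectomy rate.
- Risk of complication among those operated on, *r*: not given. Assumed 50%, with 30% and 60% as alternatives.
- Operated share, *s*: not given. Assumed range 50% to 100%.

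**Formula**

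Reported rate = (operated × *r*) / treated = *r* × *s*, where *s* = operated / treated.

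**Results at *r* = 50%, all planned participants treated**
- 16 of 18 operated on: 8/18 = 44.4%, a shortfall of 5.6 points.
- 14 of 18: 7/18 = 38.9%, a shortfall of 11.1 points.
- 12 of 18: 6/18 = 33.3%, a shortfall of 16.7 points.
- Group C, 8 of 9: 4/9 = 44.4%, the same as 16 of 18.

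**Results over the assumed range**

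| Assumed *r* | *s* = 100% | *s* = 88.9% | *s* = 70% | *s* = 50% |
|---|---|---|---|---|
| 30% | 30% | 26.7% | 21% | 15% |
| 50% | 50% | 44.4% | 35% | 25% |
| 60% | 60% | 53.3% | 42% | 30% |

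**Between groups.** If every group is at the planned pair share, all show 44.4% and there is no artificial difference. If one group has 16 of 18 operated on and another 12 of 18, they show 44.4% and 33.3%: 11.1 points apart at identical surgical risk.

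**On the operated base**, the reported rate equals *r* in every group, whatever *s* is.

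**The case against.** Several points against the concern carry weight.

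- **Incidence per treated participant is a legitimate summary.** It describes the burden across everyone who started treatment. This stands, and is a reason to keep that percentage beside the new one. It does not make it the rate after surgery.
- **Operated participants are selected after randomisation.** If toxicity removes frailer participants before surgery, the operated-only rate is selected too. This stands. The operated base removes the dilution but does not make the groups comparable.
- **A reader could rebase the counts.** Disposition gives the number operated on, and Listing 2.1.3 covers radical cystectomy. But disposition follows the FAS and assigned group, while safety follows actual treatment, so the two numbers need not match.
- **Toxicity before surgery is visible elsewhere.** Tables 3.2.18, 3.2.19, 3.6.1 and 3.6.2 cover treatment discontinuation and delay of surgery. This stands, and it limits the harm.
- **The shells are separate and Appendix A calls its lists guidelines.** A shell might use another denominator, and that cannot be checked here. The rule in Section 5.3.6 is in the body of the SAP, however, so an operated-only base would need a stated exception.

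Some stronger readings are not supported:

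- A reader might infer that the group with the fewest operations is diluted most. Dilution follows the proportion, not the number: Group C is the smallest by design, yet 8 of 9 is diluted exactly as much as 16 of 18.
- A reader might take an 11-point artefact as expected. Nothing in the SAP points to operated shares as unequal as 16/18 and 12/18. Section 3 only provides for the case that surgery does not happen.
- A reader might conclude that a required Clavien-Dindo table is missing. Section 8.2.2 calls for classification, not tabulation, and Listings 2.7.6 and 2.7.9 cover these events.

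**Conclusion.** The point holds. As written, the SAP counts treated participants who never had a cystectomy in the denominator for post-cystectomy complications, and the reported percentage falls in proportion to the share operated on.

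The size is unknown, because the SAP gives neither a cystectomy rate nor a complication rate. At an assumed 50% risk and the planned paired-biopsy share, the understatement is 5.6 points and equal across groups. It grows to 16.7 points if only 12 of 18 are operated on. A difference between groups appears only if their operated proportions differ.

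The table is descriptive, so no test, sample size or primary conclusion is affected. Nor would either denominator show whether neoadjuvant treatment raises surgical morbidity, since none of the five groups has surgery without study treatment. This is a cheap improvement to a reported safety rate.

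**What to change.** In Section 8.2.3 and Table 3.2.20, show for each group, by actual treatment, the number of Safety Population participants who underwent radical cystectomy, and give the percentages on that number. Keep the Safety Population percentage alongside if wanted, labelled as incidence per treated participant. In Section 5.3.6, note the exception and say that operated participants are a post-randomisation subset, so their rates are descriptive.

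The cost is one extra denominator column. Cystectomy status is already planned data (Section 6.2, Listing 2.1.3). The reported rates will be somewhat higher wherever some treated participants were not operated on.

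Optionally, add maximum Clavien-Dindo grade to the same table. Section 8.2.2 classifies these events by it, but no planned table title shows it. This is a suggestion, not the correction of an error.
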